Appendix 2 provides details of the planned methodology, including sample SAS code.

[figure not shown]

10.2. Exploratory efficacy analyses

[figure not shown]
10.2.1. Exploratory efficacy endpoints

CONFIDENTIAL

10.2.2. Exploratory efficacy analysis methods

11. Safety analyses

The safety population will be used for all safety analyses. All recorded safety parameters will be listed.

The investigator will promptly review each Adverse Event (AE) for accuracy and completeness, and classify each AE according to its intensity, its relationship to study drug or administration procedure, and its seriousness. AE will be coded using version 20.1 or later of the MedDRA dictionary. AEs will be monitored throughout the study and documented on the appropriate AE form. AEs will be categorized as ocular and non-ocular as well as by system organ class (SOC) and preferred term (PT), seriousness, severity, and relation to study medications. AEs will be summarized by subject, not event.

All AE presentations will summarize treatment-emergent adverse events (TEAEs) defined as AEs with onset on or after first dose of investigational drug or placebo.

The following presentations of AEs will be generated:

- Overall adverse events summary (including any AEs, ocular AEs, resolved ocular AEs, non-ocular AEs, TEAEs, ocular TEAEs, non-ocular TEAEs, SAEs, treatment-emergent SAEs, treatment-related treatment emergent SAEs, TEAEs by maximum severity, TEAEs by relationship to study drug, AEs leading to treatment/study discontinuation);
- Serious adverse events (SAE) by SOC and PT;
- All ocular AEs by SOC and PT;
- All non-ocular AEs by SOC and PT;
- AEs suspected to be related to the study medication;
- AEs leading to treatment discontinuation.
- AEs leading to study discontinuation.

All AE data will be presented in listings. Selected AEs will be listed for ocular TEAEs, AEs leading to treatment discontinuation, AEs leading to study discontinuation, and AEs related to the study medication. In addition, for the safety population “traffic light” plots will present reported AEs by severity over time by treatment group.

BCVA will be summarized by treatment group and study visit for both study and fellow eyes.

12. Subgroup analysis

13. Appendices

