11.4.5 Secondary Efficacy Analysis

11.4.6 Other Efficacy Analysis

11.4.7 Safety Analysis

All safety analyses will be performed on the safety population.

The safety of OC-02 will be assessed primarily by the incidence of AEs. An AE will be considered a treatment-emergent AE (TEAE) if it occurs or worsens on or after initiation of treatment. An overall summary of TEAEs will be presented including the number of events

and the number of subjects with events (along with percentages) by treatment group for TEAEs in several categories base on seriousness, relationship to treatment, and severity.

Other safety endpoints including visual acuity, slit-lamp biomicroscopy and intranasal examination will be summarized by treatment group and visit using descriptive statistics. Changes or shifts from baseline will be summarized where appropriate. For assessments performed by eye, study eye and fellow eye will be summarized separately. In addition, shifts from baseline to worst on-treatment value for ocular safety assessments will be summarized.

The SAP will present methods of analysis of these defined parameters in detail.

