This statistical analysis plan (SAP), which is based on Amendment 1.0 of the study protocol dated 11 July 2018, defines the methods and analyses that Oyster Point Pharma, Inc, (henceforth, Oyster Point) plans to use to analyze the data from Protocol OPP-003. This SAP complies with guidance promulgated by the International Conference on Harmonization (ICH) and the US Food and Drug Administration (FDA). If the protocol is subsequently amended, this SAP may be amended as well. Should the SAP and the protocol be inconsistent with respect to the planned analyses, the language of the SAP is governing.

2. Investigational plan

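### SAP Section 11 omits the event counts and the worsening clause that Protocol Section 11.4.7 plans for the TEAE summary, and gives no reason (minor)

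*SAP*

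**What the plan says.** SAP Section 11 (Safety analyses) sets the counting rule: "AEs will be summarized by subject, not event". It then sets the scope and definition: "All AE presentations will summarize treatment-emergent adverse events (TEAEs) defined as AEs with onset on or after first dose of investigational drug or placebo".

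Protocol Section 11.4.7 differs on both. On counting, it says "An overall summary of TEAEs will be presented including the number of events" and continues "and the number of subjects with events (along with percentages) by treatment group". On the definition, it says "An AE will be considered a treatment-emergent AE (TEAE) if it occurs or worsens on or after initiation of treatment".

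SAP Section 1 decides which text applies: "Should the SAP and the protocol be inconsistent with respect to the planned analyses, the language of the SAP is governing". The readable text of the SAP neither mentions nor explains either difference.

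**The concern.** The two counting rules cannot both be followed, and the precedence clause selects the SAP's. A tabulation that the protocol planned is therefore lost without comment.

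This bears on a stated aim. SAP Section 2.2 (Table 1, Objective 2) sets out to compare the safety and tolerability of the active spray and placebo. For a spray that subjects give themselves twice a day, how often a complaint recurs is part of tolerability. A subject with one episode and a subject with several separately recorded episodes of the same event count alike when only subjects are counted.

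The definition raises a second question. Without the worsening clause, an event that began before dosing and became worse afterwards could be treatment-emergent under the protocol and not under the SAP. Where that happens, the SAP's TEAE count can only be the lower of the two.

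**Working it through.** The plan gives no figure to reproduce here. The check is a comparison of text, with two small illustrations.

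**1. Event counts.** The two plans for the overall TEAE summary are:

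| | Number of events | Number (%) of subjects |
|---|---|---|
| Protocol 11.4.7 | planned | planned |
| SAP 11 | ruled out | planned |

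Only the events column differs, and the SAP governs, so that column is not produced.

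**2. What the column would show.** Protocol Section 6.1 gives twice-daily dosing for 4 weeks and about 30 active and 15 placebo subjects. Planned administrations per subject are 2 × 28 = 56. This counts doses, not events. The documents give no adverse event rate, and their readable text has no rule for when a repeat episode becomes a separate record. Assume that one subject has *k* separately recorded episodes of one event, at most one per administration, so *k* lies between 1 and 56.

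- Protocol: *k* events, 1 subject.
- SAP: 1 subject, for every *k*.

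At *k* = 1 nothing is lost. For larger *k* the SAP count does not change. By arm, the subject count cannot exceed about 30 (active) or 15 (placebo), however often events recur.

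**3. Worsening.** There are three cases:

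- *A condition present before dosing worsens after it.* Protocol Section 10.1 treats this as a new adverse event. Its onset is then post-dose, and it is a TEAE under both documents.
- *An event starts after dosing and later worsens.* It is already a TEAE under both documents, and the SAP's row for maximum severity reflects the worsening.
- *A record keeps a pre-dose onset, the event worsens after dosing, and no new record is made.* This is a TEAE under the protocol and not under the SAP. Only here do the definitions diverge.

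**4. Room for the third case.** Protocol Section 9.3.1 places consent, cotton swab stimulation, randomization and the first administration all at Visit 1, Day 1. Protocol Section 10.1 asks for the date of onset and does not mention a time. SAP Section 7.2 also counts time in days, from dates. If onset is compared with first dose by date, an event arising earlier on Day 1 shares the first-dose date and meets the SAP definition. SAP Section 7.3 (Missing and partial data) has no readable text, so any rule there cannot be seen.

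**5. Size of one reclassification.** One subject who moved out of a TEAE row would change incidence by 1/15 = 6.7 percentage points on placebo or 1/30 = 3.3 points on active. This holds only if that subject has no other event in the row. It is arithmetic per subject, not an expected effect, and it has no bearing on the missing event counts.

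**The case against.** The strongest reply is that almost nothing is lost. Protocol Section 11.4.7 rests safety mainly on incidence, and a subject with repeated events is still counted once. SAP Section 11 lists all adverse event data and plots reported events by severity over time for each arm. In a trial of about 45 subjects these can be read directly. On worsening, Protocol Section 10.1 does most of the work that the missing clause would do.

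Most of this stands. A reader might infer that repeated and worsening events disappear from the safety summaries. The documents do not support that. Repeats are lost from the counts only, and most worsening cases meet the SAP definition anyway. Nor can the 56 planned doses be read as dozens of events per subject, since no rate is given.

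A reader might also take the separate rows for any adverse events and for TEAEs in the SAP's overall summary as proof that pre-dose events are expected and then lost. The rows do suggest that such records can exist, but in that case they would still appear under any adverse events. If instead every presentation is confined to TEAEs, as SAP Section 11 also says, the separate rows prove nothing. This is loose wording, not a demonstrated loss.

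Two things survive the reply. Listings and plots do not give a number by arm, and the protocol planned one. And the reply does not explain why the SAP dropped a clause that the protocol kept alongside Section 10.1.

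**Conclusion.** The mismatch is real and its consequence is minor. The SAP drops the protocol's event count from the overall TEAE summary, so recurrence within a subject will not appear in any count by arm. Omitting that count leaves subject-level incidence unchanged.

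The definitions differ only for an adverse event record kept under a pre-dose onset. The number of such records is unknown and probably small. This assumes that sites apply Protocol Section 10.1 and enter worsened pre-existing conditions as new events. The documents do not show how the eCRF handles that, or whether onset is compared with first dose by date or by time of day.

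**What to change.** Make two changes in SAP Section 11:

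1. Replace the subject-only sentence with one stating that the overall TEAE summary gives the number of events as well as the number and percentage of subjects, by treatment group.
2. Define a TEAE as an adverse event that occurs or worsens once treatment has started, so that it matches Protocol Section 11.4.7.

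If either departure is intended, the SAP should say so and give the reason. Event counts by system organ class and preferred term are optional: the protocol promises them only for the overall summary, and they would affect more tables.

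The cost is one added column and two SAP sentences, with no new data.

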Appendix 1. Schedule of visits and measurements

Procedure	Screen/ Visit 1	Visit 2	Visit 3	Visit 4 (Day 21 ±2)	Visit 5	
	Day 1 2-6	Day 7 ±2	Days 8-13	Days 14 ±2 15-20	Pre-CAE® Post-CAE® Days 22-27	Day 28 ±2 ET
Informed consent/HIPAA	X					
Demographics	X					
Medical history, prior medication(s), ocular history and updates	X					
Eligibility criteria	X					
Urine pregnancy test	X ₄			X ₄		X ₄
OSDI® questionnaire	X				X	
Eye Dryness Score (EDS)	X				X	X ₂
████████ Ocular Discomfort Scale	X			X	X ₅	
BCVA	X ₁		X ₁	X ₆		X ₁
Slit lamp biomicroscopy	X ₁		X ₁	X ₆		X ₁
Corneal fluorescein staining	X					X ₂
Schirmer's test	X ₁		X			X
Schirmer's test with cotton swab stimulation	X					
Intranasal examination	X ₁				X	X
Randomization	X					
Administer investigational drug / placebo	X ₃	X	X ₃	X	X	X ₃
Dispense investigational drug / placebo	X		X			
Concomitant medications	X		X	X		X
AE Query	X		X	X	X	X

X₁ = Pre- and Post-treatment procedures; X₂ = Post-treatment procedures X₃ = Concurrent with Schirmer's Test; X₄ = For females of childbearing potential; X₅ = Procedure started at time 0 and then conducted every 5 minutes thereafter during the 120 minute CAE® exposure; X₆ = Procedure may be performed after CAE® exit at the Investigator's discretion as needed

CONFIDENTIAL

Appendix 2. Analysis for primary efficacy outcome with multiple imputation

[figure not shown]
[figure not shown]
[figure not shown]

[figure not shown]
Exhibit 1. Sample SAS code for assessing missing data patterns

[figure not shown]
CONFIDENTIAL

CONFIDENTIAL

[figure not shown]
Appendix 3. Sensitivity analysis using a mixed model for repeated measures

Appendix 4. Winsorized mean approach

CONFIDENTIAL

CONFIDENTIAL
